#### **Phase 1**

The primary purpose of data analysis in Phase 1 is to inform the adaptation of the YMHP intervention for delivery by Health Educators in CBO settings, and the development of CET implementation protocols. Focus group dialogue will be transcribed by a team of 10-15 undergraduate and graduate student interns at PRIDE, thematically coded by the Research Scientist and Principal Investigator using NVivo, and analyzed following procedures outlined by Miles and Huberman and Patton for thematic analysis. Our focus will be on factors that can enhance intervention acceptability and sustainability, both from the perspective of the peer counselors and participants.

#### **Phase 2**

Qualitative analysis: Interviews will be transcribed prior to data analysis. The team will use NVivo to conduct thematic content analyses to identify implementation barriers and facilitators. Using constant comparison analytic methods, a preliminary codebook will be developed both deductively and inductively. Research Scientist and another member of the team will code each interview. Divergent coding will be discussed, decision trails will be created at key decision-making junctures, and consensus-building strategies will resolve discrepancies. Findings will be used to inform revisions of the YMHP implementation package.

Statistical analysis: The primary hypothesis is that participants randomized to receive YMHP will demonstrate significant reductions in sexual risk behavior and associated health outcomes as well as substance use frequency and severity when compared to those who randomized to eTAU. We will utilize stratified block randomization with substance use and interventionist as the strata in order to assign all participants to a condition.

A series of bivariate analyses within SPSS (version 27) evaluated the success of randomization and the presence of differential attrition. With respect to randomization,  $\chi^2$  tests of independence evaluated between-condition differences across demographic characteristics (race and ethnicity, sexual identity, relationship status, education, income, and age). Where cell sizes for categorical variables were too small ( $n < 5$ ) to permit chi-square tests, we utilized a Fisher's exact test. The generalized linear model function in SPSS – which permits the specification of Poisson and negative binomial outcome variable distributions – was used to evaluate between group differences in baseline frequency of primary (marijuana use days, other illicit drug use instances, and CAS with male partners) and secondary (alcohol use days) outcomes. Likewise,  $\chi^2$  analyses were used to evaluate whether the probability of retention at each follow-up was associated with site, condition or categorical demographic factors; meanwhile, the generalized linear model component of SPSS was used to test whether retention at follow-up was associated with baseline primary or secondary outcome frequency.

Outcome analyses were conducted using piece-wise latent growth curve (LGC) models following procedures outlined by Chou et al., (Chou et al., 2010) and used previously in similar studies (Flora, 2008; Kohli et al., 2013; Li et al., 2001; Naar-King et al., 2009; Naar et al., 2020). Growth trajectories over-time following the delivery of an intervention may be characterized by a large initial response followed by a more sustained trajectory with a less dramatic slope. Piece-wise LGC models quantify this kind of trajectory through the use of two slopes. Slope 1 quantifies the change from baseline to the immediate post-test (3-month follow-up). Meanwhile, Slope 2 quantifies the trajectory over the post-intervention follow-up period.

All primary (marijuana use, other illicit drug use, and CAS with male partners) and secondary (alcohol use) outcomes were modeled as negative binomial distributions. All models were estimated using full-information maximum likelihood estimation in MPlus Version 8.0. This permitted the retention of all randomized cases consistent with a true intent to treat paradigm. Many commonly used indices of model fit are not available for growth models with count-distributed outcomes (i.e., root-mean square error of approximation (RMSEA)  $\leq 0.05$ , Tucker-Lewis fit index (TLI)  $> 0.95$ , and comparative fit index (CFI)  $> 0.95$ ). Model fit was therefore

evaluated using a robust log-likelihood  $\chi^2$  test (Satorra & Bentler, 2001) comparing the log-likelihood of the specified model to a null-model – in which all structural coefficients associated with the regression of latent growth factors on condition and site were constrained to be zero.

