##### *Primary Outcomes*

- Substance Use/Abuse
  - ASSIST
  - PRIDE Grid
  - Cannabis Use – Perceptions of Criminality
- Sexual Risk Behavior
  - Main and Casual Partners
  - Harmonized Sexual Risk Behavior
- Pre-Exposure Prophylaxis (PrEP) Uptake
  - Motivational PrEP Cascade
  - General PrEP Experiences and Acceptability
  - Decisional Balance for PrEP Use
  - PrEP Treatment Adherence
  - Perceived Risk of HIV scale (only 2 questions)
  - The Contemplation Ladder: PrEP Use

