### **6.2 Quantitative Analysis Plan**

Primary Outcome Measures:

- Days of Illicit Drug Use (past 30 days)
- Days of Marijuana Use (past 30 days)
- Condomless Anal Sex Acts (past 30 days)

Secondary Outcome Measure:

- Days of Alcohol Use (past 30 days)

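### The stated model-fit test is really a joint test of condition and site, and three two-slope primary outcomes have no deciding contrast, success rule or error control

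*Combined protocol and SAP*

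**What the plan says.** **Fit.** Section 6.2 (Phase 2, statistical analysis) fits a piece-wise latent growth curve with negative binomial outcomes to each primary and secondary measure. It notes that "Many commonly used indices of model fit are not available for growth models with count-distributed outcomes" and therefore evaluates fit by a robust log-likelihood chi-square test against a null model in which "all structural coefficients associated with the regression of latent growth factors on condition and site were constrained to be zero". It describes no other fit check.

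**Outcomes and slopes.** Section 6.2 lists three primary outcomes: "Days of Illicit Drug Use (past 30 days", "Days of Marijuana Use (past 30 days" and CAS acts over the same period. Alcohol days are secondary. The Phase 2 text uses the same three primary outcomes but describes the illicit-drug measure as "other illicit drug use instances". On the growth model it says "Piece-wise LGC models quantify this kind of trajectory through the use of two slopes": Slope 1 runs from baseline to the immediate post-test and Slope 2 covers later follow-up.

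**Hypothesis and alpha.** The primary hypothesis expects "significant reductions in sexual risk behavior and associated health outcomes as well as substance use frequency and severity" under YMHP compared with eTAU. Section 6.2.4 calculates power outcome by outcome at alpha 0.05, for proportions. It includes STI diagnoses, which section 6.2 does not list as an outcome. The instrument list in section 4.8 places "Pre-Exposure Prophylaxis (PrEP) Uptake" under its primary heading.

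**The concern.** **Part A.** A test between two nested models is informative only about what differs between them. Here that is the condition and site paths. A significant result could be reported as good fit when the shape or distribution is wrong, and a non-significant one could be read as poor fit when condition and site simply have no effect. Distribution matters because marijuana days and alcohol days cannot exceed 30, while a negative binomial has no upper limit. Whether that ceiling applies to illicit drug use depends on whether days or instances are counted.

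**Part B.** With three outcomes and two slopes each, the same results could be called positive or negative under a rule chosen afterwards. The hypothesis links sexual risk and substance use in a way that can be read as requiring both or either. Nothing elsewhere supplies a hierarchy, an alpha split, a co-primary rule or an adjustment.

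**Working it through.** **1. The plan's power figures.** Inputs from section 6.2.4: 221 retained of 260, so n = 110.5 per arm; alpha 0.05, taken as two-sided. With p̄ the mean of the two proportions,

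power = Φ{ [|p1 − p2| − z·√(2p̄(1 − p̄)/n)] / √([p1(1 − p1) + p2(1 − p2)]/n) }.

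- CAS, 0.50 v 0.30: (0.20 − 1.960 × 0.0659)/0.0645 = 1.098, power 86.4% (plan 85.4%).
- Substance use, 0.80 v 0.62: (0.18 − 1.960 × 0.0611)/0.0598 = 1.009, power 84.3% (plan 83.0%).
- STI, 0.15 v 0.04 and 0.20 v 0.07: 80.1% and 81.2%, average 80.6% (plan 81.0%).

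The figures reproduce within two points, without the plan's counselor effect.

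**2. What the fit test responds to.** Simulation with assumed data: N = 221, five visits, negative binomial with dispersion 1, no random effects, 700 runs per scenario. The plan-type test (condition and site on intercept and both slopes, 6 df) is set beside a direct 2-df test of free visit means against the two-piece shape.

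| Scenario | Plan-type test rejects | Direct shape test rejects |
|---|---|---|
| Correct shape, no condition or site effect | 6.3% | 4.9% |
| Badly wrong shape, no condition or site effect | 4.4% | 100% |
| Correct shape, site effect only | 99.3% | 4.9% |
| Wrong shape, site effect only | 97.9% | 100% |

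The plan-type test does not react to the wrong shape and reacts strongly to site alone. The site effect was a log rate of −0.4 on Slope 1. The rates depend on these assumptions; the structural point does not.

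**3. How the 30-day ceiling could matter.** Single-visit maximum-likelihood fits to assumed 0–30 distributions, with no covariates or random effects:

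| True share at 30 days | Fitted negative binomial share above 30 |
|---|---|
| 0–2% | 1–10% |
| 10% | 4–12% |
| 25% | 8–16% |
| 40% | 14–19% |

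The fitted share at exactly 30 was below 1% throughout. At n = 221 a beta-binomial out of 30 improved BIC by 42 to 714 points when at least 10% were at 30, but by −5 to 117 when 0–2% were. The documents do not give the share reporting 30 days.

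**4. False-positive rates under each possible rule.** Two-sided 0.05 tests; correlated cases by simulation.

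- Any of three, one contrast each: 1 − 0.95³ = 14.3% if independent; about 10% at between-outcome correlation 0.8. Counting only results that favour YMHP: 5–7%.
- Any of six, both slopes: 1 − 0.95⁶ = 26.5% if independent; down to 16% at between-outcome correlation 0.8 and between-slope correlation −0.7. Favouring YMHP only: 9–14%.
- All three required, one contrast each: at most 5%, because a false claim needs every test to succeed.
- Holm across three: 4.9% (correlation 0) to 3.5% (correlation 0.8) under the null.

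**5. Power under each rule.** Step 1 powers, with the substance-use inputs used for both drug outcomes (an assumption: the plan has one substance-use calculation) and correlation 0 to 0.8.

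- Holm's first step alone (alpha 0.05/3 = 0.0167, z = 2.394): CAS (0.20 − 2.394 × 0.0659)/0.0645 = 0.654, power 74%; substance use 71%. This is the worst case.
- Full Holm: CAS 80–83%, each drug outcome 78–81%, at least one success 85–98%.
- All three at unadjusted 0.05: 0.864 × 0.843 × 0.843 = 61% if independent, about 75% at correlation 0.8.

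**The case against.** **The fit test has little consequence.** The plan does not use it to judge YMHP, it follows a cited procedure that cannot be seen here, and RMSEA, TLI and CFI are indeed unavailable for these models. All of that stands, and it limits Part A to a false statement about fit. It does not rescue the test: observed-versus-implied means and BIC comparisons remain available and are not planned.

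**The negative binomial may be adequate.** This stands when few participants report 30 days. The BIC gaps come from single-visit fits without growth factors and do not carry over to the repeated-measures model. A reader might infer that the ceiling biases the treatment effect; nothing here shows that.

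**The 16–26% needs an any-of-six rule that no section states.** Correct. A reader might take 26% as the trial's error rate. The documents do not support that, since the hypothesis can equally be read as requiring every outcome, with no inflation. What stands is that the rule is unstated.

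**The primary set is largely settled.** A reader might infer from section 4.8 and section 6.2.4 that PrEP uptake and STI are rival primary outcomes. The outcome list and the Phase 2 text name the same three, and the revision history's last entry is the statistical update. Section 4.8 groups survey instruments by domain; its primary heading even covers a cannabis-perception measure scheduled at baseline only. This is a wording inconsistency, not an open choice of endpoints.

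**Conclusion.** The point holds in two parts of unequal weight.

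Part A is wrong as written. The comparison described is an omnibus test of condition and site and cannot establish that the growth shape or count distribution fits. The remedy is a relabelling plus real checks. How badly the negative binomial might fit is unknown.

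Part B carries the weight and should be fixed. With no deciding contrast, success rule or error control, the false-positive rate could be at most 5%, 10–14% or 16–26%, depending on a rule the plan leaves open. These ranges assume two-sided 0.05 tests and between-outcome correlations of 0 to 0.8. The power figures are indicative only, because section 6.2.4 uses proportions and the analysis uses counts.

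**What to change.** **Part A.**
- Relabel the test as an omnibus test of condition and site.
- Judge fit by observed versus model-implied means at each visit and, for day counts, by the share at 0, at 30 and above 30.
- Keep the negative binomial as primary. Add a bounded (out of 30) sensitivity model for marijuana and alcohol days, and for illicit drug use if reconciling days with instances shows that it is a day count.

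**Part B.**
- Name one condition contrast per primary outcome that measures change from baseline: Slope 1, or a post-baseline contrast with condition's path to the intercept fixed at zero or subtracted. As worded, the growth factors regressed on condition include the intercept, so a plain average over follow-up would carry any baseline difference.
- Reconcile whether 12-month data are used. The abstract's duration entry says that visit was removed in May 2020, but the abstract's data-collection entry and sections 4.2, 4.6 and 6.2.4 keep it.
- State whether any or all primary outcomes must succeed; apply Holm if any one suffices. Report other slope results as descriptive.
- Bring PrEP uptake (section 4.8) and STI (section 6.2.4) into line with the section 6.2 list.

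**Cost.** SAP wording and a few extra model runs per outcome; the bounded model may need software other than Mplus. Either success rule costs power, as step 5 of the working shows, so the choice should be made with both sets of figures in view. The Phase 2 analysis text is largely in the past tense and the SAP update is dated 10.1.2021. If results have been seen, these choices must be labelled post hoc, which weakens the claim they support.

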#### **4.1.2 CASI**

After obtaining informed consent, participants will complete a confidential computer-based survey (CASI) at the CBO site that will ask about their substance use, sexual behavior, and general thoughts and feelings. CBO study staff will administer the baseline CASI survey on a study-designated iPad or computer and ensure the participant can complete the survey in a quiet place. The participant will be able to reach the assessor if they have any questions or encounter errors completing the survey, but the assessor will not be in the room so that the participant completes the CASI in private. The baseline CASI will take about 45 minutes to complete.

Participants who screen ineligible based upon CASI responses will be dropped from the study and all relevant databases. They will be given a \$25 gift card for completing the CASI. This was changed in August, 2019 because too many participants were incorrectly answering study eligibility questions on the BL CASI. After that point, Study eligibility was determined at screening.

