#### 4.1.4 Randomization

Participants will be randomized at the end of their baseline assessment into one of two intervention conditions: 1) delivery of the 4-session YMHP intervention or 2) delivery of a single eTAU session. Each participant's condition will be tracked in the REDcap database maintained by the Research Coordinator.

To assign condition, the study employs a stratified block randomization procedure with strata for interventionist and substance use. Interventionists are crossed by condition rather than nested, allowing for a more statistically powerful design. The assigned interventionist will be used for these particular strata. The substance use strata will randomize based on whether the participant used only marijuana in the past 3 months versus use of another drug in the past 3 months. After a participant completes the CASI, the assessor will open the randomizer in Qualtrics. The assessor will enter the participant's ID, the assigned interventionist, and select either "marijuana-only" or "other substance use" into the randomizer. The block randomization procedure will select the condition.

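### The randomisation strata are not specified in the outcome models, and demographic covariates enter by baseline significance test instead of prognostic value

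*Combined protocol and SAP*

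**What the plan says.** **Randomisation.** Section 6.2 (Phase 2) states: "We will utilize stratified block randomization with substance use and interventionist as the strata in order to assign all participants to a condition". Section 4.1.4 defines the substance stratum: "The substance use strata will randomize based on whether the participant used only marijuana in the past 3 months versus use of another drug". The assessor enters "the assigned interventionist, and select either" one of two substance categories, so both values are on record. The same section adds: "Interventionists are crossed by condition rather than nested".

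**Outcome models.** Section 6.2 (Phase 2) describes piecewise latent growth curve models with negative binomial outcomes. It gives no covariate list. Predictors of the growth factors appear only in the description of the null model, in which "all structural coefficients associated with the regression of latent growth factors on condition and site were constrained to be zero".

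**Power.** Section 6.2.4 put a counselor random effect, for about 12 counselors, in every simulated model.

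**Covariates.** Section 6.2.3 tests for baseline differences between conditions and carries significant demographic factors into the outcome analyses, without giving a significance level. Section 6.2 (Phase 2) lists the characteristics tested as "demographic characteristics (race and ethnicity, sexual identity, relationship status, education, income, and age". Neither stratum is among them.

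**The concern.** When allocation is balanced within strata, the analysis should normally carry those strata. If they predict outcome and are left out, the standard error ignores the balance that the design achieved and precision is lost. Here the powered model had an interventionist term and the described analysis has none, with no reason given.

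The rule in section 6.2.3 is a separate weakness. Under correct randomisation every significant baseline difference is a chance event, so the rule picks covariates by chance. What makes a covariate worth including is that it predicts outcome, and the rule takes no account of that. It also means that the covariates of the primary models, for three primary outcomes, are not settled until baseline data are seen. At stake are some precision and the reader's ability to tell which model was primary.

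**Working it through.** **1. The plan's own power figures.** Inputs from section 6.2.4: 221 analysed (85% of 260), so 110.5 per arm; α = .05, taken as two-sided. Formula: power = Φ{[|p1-p2| - 1.96·√(2p̄(1-p̄)/n)] / √([p1(1-p1)+p2(1-p2)]/n)}.
- CAS, .50 v .30: (.200 - 1.96 × .0659)/.0645 = 1.10, power 86.4% (stated 85.4%).
- Substance use, .80 v .62: (.180 - 1.96 × .0610)/.0598 = 1.01, power 84.3% (stated 83.0%).
- STI: 80.1% and 81.2%, average 80.6% (stated 81.0%).

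All agree within 2 points. Omitting the strata does not alter these figures.

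**2. Can the significance rule bring the strata in?** Section 6.2.3 adds demographic factors. The six characteristics listed in section 6.2 include neither interventionist nor substance stratum. So the rule, as worded, does not reach them.

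**3. How often the rule acts.** Six independent tests at an assumed .05: 1 - .95⁶ = 1 - .735 = 26.5%. If two of the six are prognostic, at least one of those enters with probability 1 - .95² = 9.8%. If all six tests were fully correlated, the 26.5% would fall to 5%.

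**4. What the rule gains.** Simulation with a linear outcome, N = 221, six independent covariates, two of them prognostic, 6,000 replicates per setting:

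| Joint R² (assumed) | Unadjusted | Section 6.2.3 rule | Two prognostic covariates fixed in advance |
|---|---|---|---|
| 5% | 79.9% | 79.8% | 81.6% |
| 10% | 79.8% | 79.9% | 83.3% |
| 20% | 80.4% | 80.8% | 87.6% |

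Monte Carlo error is √(.8 × .2/6000) = 0.5 points, so the rule cannot be told apart from no adjustment. Type I error was 4.4% to 5.0%. An analytic check of the last column: 80% power corresponds to 1.960 + 0.842 = 2.802 standard errors, and adjustment divides the standard error by 1/√(1-R²). Power is then Φ(2.802/√(1-R²) - 1.960), which gives 80.8%, 82.0%, 84.0% and 87.9% for R² of 2%, 5%, 10% and 20%.

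**5. What the strata gain in the planned type of model.** Simulated piecewise negative binomial growth model with 260 participants, retention 97/94/91/88% through 9 months (section 4.4) and 12 crossed interventionists. The remaining inputs are assumptions: blocks of 4, random intercept SD .9, random Slope 1 SD .5, dispersion .8, and the means. There were 178 replicates per scenario. Ratio of the standard error of condition on Slope 1, with the stratum against condition and site only:
- CAS-type outcome: .992, a change of -0.8%.
- Other illicit drug use, four scenarios: 1.011, .934, .960, 1.005, so -6.6% to +1.1%. The two reductions come from scenarios with 5% discordance between entered stratum and reported use, with the stratum on intercept and slopes. The two small increases come from scenarios with no discordance and the stratum on slopes only.
- Interventionist as fixed effects on intercept and Slope 1 (assumed SD .2 on each), CAS-type outcome: .975, a change of -2.5%. A random intercept was not simulated.

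**6. Why other illicit drug use differs.** The outcome is "Days of Illicit Drug Use (past 30 days", and the marijuana-only stratum is defined by no other drug in the past 3 months, so its baseline mean should be near zero. It need not be exactly zero: the stratum is entered by hand, and section 4.1.2 records that "too many participants were incorrectly answering study eligibility questions on the BL CASI". With 5% discordance the stratum's intercept coefficient was estimable (about -4.1 and -4.5, standard errors about .4). With none, it separated.

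**The case against.** **The effect is small.** This stands. The stratum changes the standard error by a few percent at most and sometimes not at all, and no simulation here shows excess false positives. Precision alone would make this a minor point. What remains is that the plan states an inferior selection rule, and that a better one costs almost nothing.

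**The null-model sentence is not a covariate list.** This also stands. A reader might infer that the strata were deliberately excluded. The documents support only that they are not specified. Section 6.2.2 also speaks of characteristics needing adjustment without confining them to demographics, but it describes monitoring of randomisation and names no model term.

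**Section 6.2.3 may be inherited text.** It is in the future tense, while the model description is in the past tense, and the statistical plan was updated in October 2021. Whether the rule governed the models that were run is unclear. That is a reason to settle its status.

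**Site already covers part of interventionist.** True, because Health Educators belong to a CBO. But section 2.2 plans at least two per CBO, so site cannot stand in for interventionist. The figure of 12 is a planning assumption, and one CBO left in May 2019. With few interventionists a variance term may be poorly estimated.

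**The fixed-list gain is assumed.** It presumes that the prognostic covariates are known, and it uses the 12-month N although that visit was removed in May 2020. The growth model already contains the baseline count, so demographics may add less.

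**A larger loss might be inferred.** A simpler simulation (normal outcome, no baseline measure, assumed strata shares of 5%/2% to 30%/5% of variance) gives type I error of .042 falling to .021 and a power loss of about 2 to 9 points when strata are omitted. The documents give no variance shares, and that model lacks the baseline count, so these figures should not be applied to the planned analysis.

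**Conclusion.** The point holds in a limited form. Two stratification factors are not specified in the outcome models, the interventionist term used for power is missing from the described analysis, and demographics are admitted by a rule that gains nothing over no adjustment. The consequences are modest lost precision and covariates left open until data are seen. Nothing here indicates bias towards YMHP or inflated type I error.

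The sizes depend on assumptions that the documents do not supply: about -7% to +1% in the standard error for the stratum, and about 0 to 8 power points for a fixed list at an R² of 2% to 20%, possibly less with the baseline count in the model. The 26% assumes independent tests at .05. The text comparison is firm and the magnitudes are of medium confidence. The change should be made, but the trial does not depend on it.

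**What to change.** 1. In section 6.2 (Phase 2), list the covariates of every model. Add the substance stratum, as entered in the randomiser, as a fixed covariate of the slopes for every outcome, and of the intercept for every outcome except other illicit drug use. Decide this in advance, so that the model does not depend on whether a coefficient proves estimable. For that outcome it gives up the 4% to 7% reduction seen with the stratum on the intercept as well. Using the entered value also covers participants who qualified on heavy drinking alone, whom neither randomiser category describes.
2. Keep site, and account for interventionist in line with section 6.2.4: a random intercept, or fixed effects if the number of interventionists is small.
3. Replace the rule in section 6.2.3 with a short fixed list of baseline covariates chosen for prognostic value. Report baseline balance descriptively.
4. If the models have already been run, keep them as run, show the adjusted models beside them, and label each as specified before or after the data were seen.

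**Cost.** Revised wording, reruns and a few extra parameters per outcome; no new data are needed. If results are already known, the adjusted models are post hoc and can only be supportive.

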### **6.2.4 Power Analysis**

We will enroll a total of 260 substance-using MYMSM (130 per condition) engaged in HIV risk behavior; this will be 1.8 times more participants than in the original efficacy trial, providing adequate power to detect differences in this real-world setting. We conducted a series of simulations using SAS 9.2 PROC GLIMMIX to examine power to detect intervention effects on primary outcomes. In each simulation, 500 draws were requested and effects averaged across samples assuming 260 enrolled participants with retention of 85% at 12-month follow-up (n = 221). All models included a random effect for counselor assuming approximately 12 peer counselors across sites by the end of the study. Consistent with existing CDC and NYCDOH data on 12month STI incidence among MYMSM, we allowed the proportion of positive diagnoses in the eTAU/YMHP groups to vary between 0.15/0.04 and 0.20/0.07, respectively, and found 81.0% average power (i.e.,  $1 - \beta$ ) to detect statistically significant differences at  $\alpha = 0.05$  (i.e., 95% confidence). Utilizing the effect sizes found within the original YMHP efficacy trial (that utilized an intensive attention-control group), we set the proportion of individuals in the eTAU group who engaged in CAS at follow-up to 0.50 and to 0.30 in the YMHP group and found 85.4% power to detect significant differences at  $\alpha = 0.05$ , suggesting effects of this magnitude or larger will be sufficiently powered. Finally, examining substance use, assuming that the proportion of individuals in the eTAU group who persist in substance use over time is .80, we will have power to detect proportions of .62 or smaller in the YMHP group as statistically significant with power of 83.0% or greater at  $\alpha = 0.05$ .

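### The growth model appears to estimate a baseline arm difference that randomisation makes zero; fixing it at zero would sharpen the Slope 1 treatment effect at almost no cost

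*Combined protocol and SAP*

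**What the plan says.** The statistical analysis under Phase 2 of section 6.2 uses a piecewise latent growth curve. The first slope runs from baseline: "Slope 1 quantifies the change from baseline to the immediate post-test (3-month follow-up"). The second follows: "Slope 2 quantifies the trajectory over the post-intervention follow-up period". All primary and secondary "outcomes were modeled as negative binomial distributions". Estimation is by full-information maximum likelihood, so every randomised participant is kept.

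Model fit is judged by comparing the fitted model with a null model in which "all structural coefficients associated with the regression of latent growth factors on condition and site were constrained to be zero". That sentence is the only place where the plan shows how treatment enters the model: condition and site predict the latent growth factors. The intercept factor is not named, its time coding is not given, and no coefficient is identified as the primary treatment effect.

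On timing, section 4.1.4 says: "Participants will be randomized at the end of their baseline assessment into one of two intervention conditions". On baseline differences, section 6.2.3 adds demographic factors to the outcome models, and only if a baseline comparison is significant. No section sets the arms' baseline outcome means equal, uses the baseline outcome as a covariate, or regresses the slopes on the intercept.

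**The concern.** A growth curve whose first slope starts at baseline needs an intercept factor for the baseline level. If the growth factors are regressed on condition and nothing exempts the intercept, the model estimates an arm difference in the baseline outcome.

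In this trial that difference is known in advance. Baseline is measured before allocation, so any observed arm difference is chance and its expectation is zero. Estimating it spends information on a known quantity and passes the noise into Slope 1, which is measured from that baseline. What is at stake is precision: a wider interval and lower power for the early treatment effect than the same data could give.

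**Working it through.** **Inputs from the documents.** 260 participants, 130 per condition, and alpha 0.05 (section 6.2.4; two-sided is assumed because sidedness is not stated). Retention of 97%, 94%, 91%, 88% and 85% over the five follow-ups (section 4.4). Randomisation after baseline (section 4.1.4). The growth model as described above.

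**Inputs that are assumed.** The baseline-to-follow-up correlation r, the variance components, the count means, the dispersion and the rate ratios. The documents give none of these for the growth model.

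**The plan's own power figures.** With 221/2 = 110.5 per arm and the usual two-proportion formula (pooled variance under the null, no continuity correction):
- CAS, 0.50 against 0.30: 86.4% (stated 85.4%).
- Substance use, 0.80 against 0.62: 84.3% (stated 83.0%).
- STI, average of 0.15/0.04 and 0.20/0.07: 80.6% (stated 81.0%).

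These reproduce within 2 points. They concern binary outcomes at follow-up and do not involve the growth model, so they neither support nor weaken the point.

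**Step 1: two waves, linear approximation.** Let D0 and D1 be the arm differences at baseline and post-test, with equal variances and correlation r. In units of the variance of one such difference:
- Intercept path free: the contrast is D1 − D0, with variance 2(1 − r).
- Intercept path fixed at zero: the contrast is D1 − r·D0, with variance 1 − r².
- Ratio, free to constrained: 2(1 − r)/(1 − r²) = 2/(1 + r).

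For an effect with 80% power under the constrained model, power under the free model is Φ[(1.960 + 0.842)/√ratio − 1.960]. At r = 0.5 this is Φ(2.802/1.155 − 1.960) = Φ(0.466) = 67.9%. The information-equivalent sample size is 260 × (1 + r)/2.

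| r | 2(1 − r) | 1 − r² | Ratio | Power, free model | 260 is worth |
|---|---|---|---|---|---|
| 0.3 | 1.40 | 0.91 | 1.54 | 61.7% | 169 |
| 0.5 | 1.00 | 0.75 | 1.33 | 67.9% | 195 |
| 0.7 | 0.60 | 0.51 | 1.18 | 73.3% | 221 |
| 0.9 | 0.20 | 0.19 | 1.05 | 78.0% | 247 |

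The 221 here has no connection with the retained sample in section 6.2.4. Below r = 0.3 the ratio is larger still: 2/1.2 = 1.67 at r = 0.2.

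**Step 2: the piecewise structure, linear.** Generalised least squares for intercept, Slope 1 and Slope 2 was run over 5 or 6 waves. Intercept variance was 1, Slope 1 variance 0.01 to 1, Slope 2 variance 0.001 to 0.05 and residual variance 0.2 to 2. Freeing the intercept path multiplied the Slope 1 variance by 1.07 to 1.65, so 80% power falls to between 78% and 59%.

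**Step 3: negative binomial with a log link.** Five waves were used, with retention of 100%, 97%, 94%, 91% and 88%. Baseline mean was 3 or 10, dispersion 0.3 or 0.8, intercept variance 0.3 or 0.8, Slope 1 variance 0.2 or 0.4, and Slope 2 variance 0.01 or 0.02. The rate ratio was 0.8 for change common to both arms and 0.75 for treatment. The variance ratio was 1.12 to 1.59, so 80% falls to between 75% and 60%. For example, with mean 10, dispersion 0.3 and variances 0.8, 0.2 and 0.01, the standard error is 0.175 free and 0.162 constrained. That is a ratio of 1.17 and power of 73.4%.

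Steps 2 and 3 approximate the planned model; they are not fits of it in the plan's software. In every setting examined the free model was less precise.

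**The case against.** The strongest reply is that the intercept path is inferred. In the sentence about the null model, the word all qualifies the coefficients, not the growth factors, and the only factors the text names are the two slopes. If condition predicts only the slopes, there is no loss. This stands as a limit on the point. But a slopes-only reading would also take site off the intercept, which would be unusual and would normally be stated. On either reading, the reader cannot tell which model was specified.

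The plan is also silent on whether Slope 1 is regressed on the intercept. If it is, the contrast is baseline-adjusted and some or most of the loss may go, depending on how slope and intercept are related and how noisy the baseline count is.

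A reader might draw four stronger conclusions that the documents do not support:
- **That the treatment effect is biased or its test invalid.** Under randomisation, the free and constrained models target the same effect.
- **That Slope 1 becomes a pure change-score contrast.** This is exact only for two waves. Here later visits also inform Slope 1 through the linear Slope 2, and effects are on the log scale.
- **That a chance baseline difference contaminates the treatment test through the likelihood comparison.** Section 6.2 presents that comparison as a check of model fit, used because the usual indices are unavailable. It also removes the site paths, so it does not isolate treatment.
- **That the trial's stated power is wrong.** Those figures come from a different, binary calculation.

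Stratified randomisation limits chance imbalance in drug use. The stratum is not stated to be in the outcome model, however, so it does not recover the precision.

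**Conclusion.** The point holds as an avoidable loss of precision. On the standard reading, the model leaves free a baseline arm difference that the design makes zero, and nothing else in the plan uses the baseline outcome to recover the loss. The Slope 1 variance is inflated by a factor of about 1.05 to 1.65 for two-wave correlations of 0.3 to 0.9 and over the multi-wave settings examined. The size depends on correlations and variance components that the documents do not give; at a high correlation it is small. The conclusion also assumes that the intercept is located at baseline, that condition has a path to it, and that the slopes are not already regressed on it. The calculation concerns Slope 1 only. This is a free improvement, not an error that invalidates the analysis.

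**What to change.** In section 6.2:

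1. State the time coding, with the intercept at baseline. The constraint is correct only under that coding; with the intercept at a later visit it would remove treatment effect.
2. Fix the condition-to-intercept path at zero. Regressing the slopes on the intercept alongside condition is an alternative route to a baseline-adjusted contrast. The constraint is simpler, because that regression adjusts for the latent rather than the observed baseline level.
3. Keep site on the intercept and add the substance-use stratum from section 4.1.4, which the stated model does not contain.
4. Name the condition-to-Slope 1 and condition-to-Slope 2 coefficients as the treatment test. If a likelihood-ratio test is used for treatment, compare with a null model that drops only those two paths and keeps site.

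The cost is a few sentences in the plan and a small change to the model syntax, with no new data. Much of this section is in the past tense. If the outcome analyses have already been run, keep the specified model as it was and report the constrained model as a documented sensitivity analysis.
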